6.3 Lost to Follow-Up

A subject will be considered lost to follow-up if they fail to return for a scheduled visit and are unable to be contacted by study personnel.

The following actions must be taken if a subject fails to return to a site for a required visit:

- The site will attempt to contact the subject and reschedule the missed visit. The site will counsel the subject on the importance of maintaining the assigned visit schedule and ascertain if the subject wishes to and/or should continue in the study.
- Before a subject is deemed lost to follow-up, the Investigator or designee will make every effort to regain contact with the subject (where possible, 3 telephone calls and, if necessary,

a certified letter to the subject's last known mailing address or local equivalent methods). These contact attempts should be documented in the subject's medical record or study file.

- Should the subject continue to be unreachable, the subject will be considered to have withdrawn from the study with a primary reason of lost to follow-up.

CONFIDENTIAL

7 Study Procedures

Written informed consent and relevant privacy authorization(s) will be obtained from all subjects before any procedures related to the study are performed. The Schedule of Procedures and Assessments ([Appendix 1](#): Schedule of Procedures and Assessment) lists the procedures that should occur at each study visit.

7.1 Visit Descriptions

Procedures should be performed in the order listed; procedures followed by an “*” may occur at other times during the visit, if needed, to accommodate site operations and/or subject bodily functions, provided the procedure is completed before in-clinic administration of IP.

7.1.1 Visit 1 (Screening; Day -30 to Day -1)

The following procedures will be performed at Visit 1 (Screening; Day -30 to Day -1):

- Explain the purpose and conduct of the study to the subject, answer subject questions, and obtain written informed consent and privacy authorization(s)
- Obtain information, including: demographics, concomitant medications, and ocular and systemic medical and medication history and surgical history
- Heart rate and blood pressure
- Subject administration of test eye drop
- Pain score training
- BCVA
- Slit lamp biomicroscopy
- IOP
- Dilated ophthalmoscopy
- Urine pregnancy test (only for WOCBP)*
- Abbreviated physical examination*
- Determine study eligibility based on Inclusion/Exclusion criteria

7.1.2 Visit 2 (Day of Surgery; Day 0)

At Visit 2 (Day of Surgery; Day 0), subjects will undergo routine CELR surgery via phacoemulsification extraction and implantation of an intraocular lens. Investigators should use their standard procedure for routine cataract surgery.

Limbal relaxing incisions (laser-assisted and non-laser) and intracameral injections and medications are allowed during the surgery. (**Note:** Corticosteroids, oral or topical NSAIDs

CONFIDENTIAL

[excluding low-dose acetylsalicylic acid], and Omidria® [i.e., phenylephrine and ketorolac injection] are prohibited.)

All medications given to subjects as part of the cataract surgery procedure, including but not limited to sedatives, local anesthetics, and topical antibiotics, should be recorded in the eCRF as concomitant medications.

After the cataract surgery, subjects should not be provided with any prescription or over-the-counter pain medication, or medications intended to minimize ocular inflammation. Subjects will be assessed for safety and randomized at Visit 3 (Baseline/Randomization; Day 1).

The following procedures will be performed at Visit 2 (Day of Surgery):

- AE monitoring
- Concomitant medication update
- Urine pregnancy test (only for WOCBP)*
- Cataract surgery

7.1.3 Visit 3 (Baseline/Randomization; Day 1)

The following procedures will be performed at Visit 3 (Baseline/Randomization; Day 1):

- AE monitoring
- Concomitant medication update
- Pain score training
- Numeric Pain Rating Scale (NPRS)
- BCVA
- Slit lamp biomicroscopy
- IOP
 - **Note:** The IOP procedure requires the administration of proparacaine 0.5% to the eye before testing; there should always be ≥ 30 minutes between the administration of topical anesthetic and IP.
- Determine study eligibility based on Inclusion/Exclusion criteria
- Randomization
- Dispense IP
- Provide instructions for IP use, dosing adherence, and dosing diary entries
- Supervised first dose of IP
- Schedule or confirm next visit and remind subject to return with dosing diary

7.1.4 Visit 4 (Day 3 \pm 1)

The following procedures will be performed at Visit 4 (Day 3 \pm 1):

CONFIDENTIAL

- AE monitoring
- Concomitant medication update
- NPRS
- BCVA
- Slit lamp biomicroscopy
- IOP
- Review dosing adherence and dairy entries
- Schedule or confirm next visit and remind subject to return with IP and dosing diary

7.1.5 Visit 5 (Day 7 ± 1)

The following procedures will be performed at Visit 5 (Day 7 ± 1):

- AE monitoring
- Concomitant medication update
- NPRS
- BCVA
- Slit lamp biomicroscopy
- IOP
- Collect unused IP
- Review dosing adherence and dairy entries
- Dispense IP
- Schedule or confirm next visit and remind subject to return with IP and dosing diary

7.1.6 Visit 6 (End of Treatment; Day 14 ± 2)

The following procedures will be performed at Visit 6 (End of Treatment; Day 14 ± 2):

- AE monitoring
- Concomitant medication update
- NPRS
- BCVA
- Slit lamp biomicroscopy
- IOP
- Collect unused IP
- Review dosing adherence and dairy entries
- Urine pregnancy test (only for WOCBP)*
- Schedule or confirm next visit

7.1.7 Visit 7 (End of Study; Early Termination; Day 21 ± 2)

The following procedures will be performed at Visit 7 (End of Study; Early Termination; Day 21 ± 2):

- AE monitoring
- Concomitant medication update
- BCVA
- Slit lamp biomicroscopy
- IOP
- Dilated ophthalmoscopy
- Urine pregnancy test (only for WOCBP)*
- Release subject from study

7.1.8 Unscheduled Visits

Safety procedures and efficacy assessments conducted at unscheduled visits are at the discretion of the Investigator. Information will be collected during unscheduled visits about changes to concomitant medications and any AEs experienced since the last visit.

If a subject reports their supply of IP to be lost, destroyed, or unusable due to unacceptable temperature excursions, a new supply of IP may be dispensed to the subject.

7.1.9 Early Termination

In the event that a subject withdraws or is terminated from the study before the end of the study, every attempt will be made to ensure that the subject returns to the site as soon as possible and completes the Visit 7 (End of Study; Early Termination) assessments before being discharged from the study. Any unused IP should be collected during an early termination visit.

CONFIDENTIAL

8 Study Assessments

The Schedule of Procedures and Assessments ([Appendix 1](#): Schedule of Procedures and Assessment) provides a list of study assessments and evaluations to be performed and the timing of each.

8.1 Efficacy Evaluations

Efficacy assessments will be conducted at the timepoints indicated on the Schedule of Procedures and Assessments ([Appendix 1](#): Schedule of Procedures and Assessment) and as detailed in the corresponding appendices. The efficacy assessments selected for the study are common tools within the field of ophthalmology and are generally recognized as reliable, accurate, and relevant in assessing the health and function of human eyes. Efficacy assessments in the study include:

- Slit lamp biomicroscopy ([Appendix 3](#): Slit Lamp Biomicroscop)
 - Ocular inflammation (Standardization of Uveitis Nomenclature [SUN] Scale)
- Numeric Pain Rating Scale ([Appendix 4](#): Numeric Pain Rating Scale (NPRS))

8.2 Safety Evaluations

Safety assessments will be performed at the timepoints indicated on the Schedule of Procedures and Assessments ([Appendix 1](#): Schedule of Procedures and Assessment) and as detailed in the corresponding appendices. The safety assessments selected for the study are all common tools within the field of ophthalmology and are generally recognized as reliable, accurate, and relevant in assessing the health and function of human eyes. Safety assessments in the study include:

- AE monitoring (ocular and non-ocular)
- Pregnancy test (urine; only for WOCBP as defined in [Appendix 2](#): Woman of Childbearing Potential (WOCBP))
- Best corrected visual acuity ([Appendix 5](#): Best Corrected Visual Acuity (BCVA))
- Slit lamp biomicroscopy ([Appendix 3](#): Slit Lamp Biomicroscop)
- Intraocular pressure ([Appendix 6](#): Intraocular Pressure (IOP))
- Dilated ophthalmoscopy ([Appendix 7](#): Dilated Ophthalmoscop)

8.2.1 Adverse Events and Serious Adverse Events

AEs will be monitored throughout the study. Subjects will be encouraged to report any adverse findings during the study, whether or not they are related to IP. These can be collected either in an unsolicited fashion without any prompting or in response to a general question such as: “Have you noticed anything different since you started the study; began the IP, etc.?”

CONFIDENTIAL

All AEs will be captured on the appropriate source documents and recorded in the eCRF. Information to be collected at minimum includes event description, onset, assessment of severity, relationship to IP, and outcome.

The Investigator will record all AEs with start dates occurring any time after informed consent is obtained until 7 (for nonserious AEs) or 30 days (for SAEs) after the last day of study participation. At each visit, the Investigator will inquire about the occurrence of AEs/SAEs since the last visit. SAEs will be followed for outcome information until resolution or stabilization.

Any medical condition that is present at the time that the subject is screened will be considered as baseline and not reported as an AE. However, if the subject's condition deteriorates at any time during the study, it will be recorded as an AE.

8.2.1.1 Definitions

An AE is any untoward medical occurrence in a subject temporally associated with the use of IP, whether or not considered related to the IP. An AE can therefore be any unfavorable and unintended sign (including an abnormal laboratory finding), symptom, or disease (new or exacerbated) temporally associated with the use of IP without any judgment on causality.

An AE is considered "serious" if it:

- Results in death
- Is a life-threatening AE

Note: An AE is "life-threatening" if, in the view of the Investigator or Sponsor, its occurrence places the subject at immediate risk of death. It does not include an AE that, had it occurred in a more severe form, might have caused death

- Requires inpatient hospitalization or prolongation of existing hospitalization
- Results in persistent or significant incapacity or substantial disruption of the ability to conduct normal life functions
- Is a congenital anomaly or birth defect

Important medical events that may not result in death, be life-threatening, or require hospitalization may be considered serious when, based upon appropriate medical judgment, they may jeopardize the subject and may require medical or surgical intervention to prevent one of these outcomes.

8.2.1.2 Classification of Adverse Events

Severity of Adverse Events

The severity of all AEs will be assessed by the Investigator and graded as follows:

CONFIDENTIAL

- **Mild:** Requires minimal or no treatment and does not interfere with the subject's daily activities
- **Moderate:** Results in a low level of inconvenience or concern and may cause some interference with functioning
- **Severe:** Interrupts a subject's usual daily activity and may require systemic drug therapy or other treatment. Severe events are usually potentially life-threatening or incapacitating. The term "severe" does not necessarily equate to "serious."

Relationship of Adverse Events

All AEs must have their relationship to IP assessed by the Investigator who examines and evaluates the subject based on temporal relationship and their clinical judgment. In a clinical study, the IP must always be suspect.

The relationship of an AE to the IP will be determined using the below categories. Final determination of AE attribution and expectedness will be determined by the Sponsor in consultation with the Medical Monitor.

- **Unrelated:** The AE is completely independent of IP administration, and/or evidence exists that the event is definitely related to another etiology. There must be an alternative, definitive etiology documented by the Investigator.
- **Unlikely:** A clinical event, including an abnormal laboratory test result, whose temporal relationship to IP administration makes a causal relationship improbable (e.g., the event did not occur within a reasonable time after administration of IP) and in which other drugs or chemicals or underlying disease provides plausible explanations (e.g., the subject's clinical condition, other concomitant treatments).
- **Possibly:** Some evidence to suggest a causal relationship (e.g., the event occurred within a reasonable time after administration of IP). However, other factors may have contributed to the event (e.g., the subject's clinical condition, other concomitant events).
- **Probably:** Evidence to suggest a causal relationship, and the influence of other factors is unlikely. The clinical event, including an abnormal laboratory test result, occurs within a reasonable time after administration of the IP, is unlikely to be attributed to concurrent disease or other drugs or chemicals, and follows a clinically reasonable response on withdrawal.
- **Definitely:** Clear evidence to suggest a causal relationship, and other possible contributing factors can be ruled out. The clinical event, including an abnormal laboratory test result, occurs in a plausible time relationship to IP administration and cannot be explained by concurrent disease or other drugs or chemicals. The response to withdrawal of the study intervention (dechallenge) should be clinically plausible. The event must be pharmacologically or phenomenologically definitive, with use of a satisfactory rechallenge procedure if necessary.

CONFIDENTIAL

Expectedness

An AE or suspected adverse reaction is considered “unexpected” if it is not listed in the Investigator’s Brochure, package insert, or device labeling, if it is not listed at the specificity or severity that has been observed, or if it is not consistent with the risk information described in the protocol, as amended. “Unexpected,” as used in this definition, also refers to AEs or suspected adverse reactions that are mentioned in the Investigator’s Brochure, package insert, or device labeling as occurring with a *class of drugs* (or other medical products) or as anticipated from the pharmacological properties or other characteristics of the IP, but are not specifically mentioned as occurring with the particular IP under investigation.

The Investigator and contract research organization, in conjunction with the Medical Monitor and the Sponsor, will be responsible for determining whether an AE is unexpected (i.e., if the nature, severity, or frequency of the event is not consistent with the risk information previously described for the IP).

8.2.1.3 Adverse Event Reporting Requirements

According to federal regulations, an Investigator must immediately report to the Sponsor any SAE, whether or not considered drug-related, including those listed in the protocol or Investigator’s Brochure and must include an assessment of whether there is a reasonable possibility that the drug caused the event.

According to federal regulations, the Sponsor must notify the US Food and Drug Administration (FDA) and all participating Investigators as soon as possible, but in no case later than 15 calendar days after the Sponsor determines that a potential serious risk arising from a clinical study qualifies for reporting. Sponsor must report any suspected adverse reaction that is both serious and unexpected. The Sponsor must report an AE as a suspected adverse reaction only if there is evidence to suggest a causal relationship between the drug and the AE (See 21 Code of Federal Regulations [CFR] 312.32[c][1]).

Furthermore, the Sponsor must also notify FDA of any unexpected fatal or life-threatening suspected adverse reaction as soon as possible but in no case later than 7 calendar days after the Sponsor’s initial receipt of the information (See 21 CFR 312.32[c][2]).

8.2.1.4 Pregnancy

Individuals who are pregnant are not permitted to participate in the study. All pregnancies are to be reported from the time informed consent is signed until the end of the study (Visit 7). Subjects who report becoming pregnant or having a sexual partner (WOCBP) who has become pregnant will have IP withdrawn, will resume standard of care treatment for their condition, and will undergo safety follow-up visits and assessments.

CONFIDENTIAL

Any report of pregnancy from a subject must be reported within 24 hours to the Sponsor or its delegate using the Pregnancy Report Form.

Every effort should be made to gather information regarding the pregnancy outcome and condition of the infant. It is the responsibility of the Investigator to obtain this information within approximately 30 calendar days after the initial notification and approximately 30 calendar days after delivery, if applicable.

Pregnancy complications such as spontaneous abortion/miscarriage or congenital abnormality are considered SAEs and must be reported to the Sponsor using the Serious Adverse Event Form. Elective abortions are not considered an SAE.

8.2.2 Heart Rate, Blood Pressure, and Other Safety Evaluations

Safety evaluations will be assessed at the timepoints indicated on the Schedule of Procedures and Assessments ([Appendix 1](#): Schedule of Procedures and Assessment). An abbreviated physical examination will be completed at Visit 1 (Screening), and heart rate and blood pressure will be checked.

CONFIDENTIAL

9 Statistical Considerations

A separate Statistical Analysis Plan (SAP) will be prepared before the database is locked and the study is unmasked and will include a more technical and detailed description of the statistical analyses described in this section. This section is a summary of the planned statistical analyses.

Continuous measures will be summarized descriptively by the mean, standard deviation, median, and minimum and maximum values. Categorical measures will be summarized by the frequency and percentage of subjects.

9.1 Statistical Hypothesis

The primary efficacy endpoint is the proportion of subjects with ACC Grade 0 in the study eye at Visit 6 (Day 14).

The Null Hypothesis: At post-operative Day 14, there is no difference in proportion of subjects with ACC Grade 0 in the study eye between an active treatment group (VVN461, 1.0%, or VVN461, 0.5%) and the Vehicle group.

Alternative Hypothesis: At post-operative Day 14, there is a difference in proportion of subjects with ACC Grade 0 in the study eye between an active treatment group (VVN461, 1.0%, or VVN461, 0.5%) and the Vehicle group.

The primary hypothesis for the study is that at least one dose regimen of VVN461 is superior to Vehicle with respect to the proportion of subjects with ACC Grade 0 in the study eye at Visit 6 (Day 14).

For the primary endpoint, a sequential testing procedure will be employed to control the overall Type I error rate at two-sided 5% with respect to multiple comparisons for the following hypotheses: VVN461, 1.0%, to Vehicle (H_1) and VVN461, 0.5%, to Vehicle (H_2). The testing procedure will be done in a hierarchical order as H_1 and H_2 . If H_1 is not significant, then H_2 will not be tested.

9.2 Sample Size Determination

A sample size of approximately 90 completed subjects will be randomized in a 1:1:1 ratio to VVN461, 1.0%, VVN461, 0.5%, and a matching Vehicle that does not contain the API. With a sample size in each group of 30, the study will have 80% power to detect a difference of 35%, assuming a response rate of 30% in the Vehicle group, and a two-sided 0.05 significance level for a Pearson chi-square test.

CONFIDENTIAL

A drop-out rate of 10% is assumed, resulting in a total sample size of approximately 102 subjects (34 for VVN461, 1.0%, 34 for VVN461, 0.5%, and 34 for Vehicle).

9.3 Analysis Populations

The Full Analysis Set (FAS) will consist of all subjects who are randomized. Subjects will be analyzed in the group to which they are randomized. This set will be used for the analysis of all efficacy endpoints as the primary analysis.

The Per Protocol (PP) Analysis Set is a subset of the FAS and will include all subjects in the FAS who complete study-required treatment and who follow the protocol without significant deviations. The determination of significant protocol deviations will be made before database lock and unmasking.

The Safety Analysis Set (SAF) will include all subjects who receive at least one dose of IP, as indicated on the dosing record. Subjects will be analyzed in the group according to the treatment received. All safety variables will be analyzed using the SAF, and only observed data will be included (i.e., missing data will remain missing for the safety analysis).

9.4 Statistical Analyses

The statistical analyses of the study will be performed on the data through Day 21, after all subjects have either completed the Day 21 visit or discontinued early from the study, and after the study database has been cleaned, verified, and locked. It is planned that the data from all sites that participate in the study will be combined so that the target sample size will be available for analysis.

9.4.1 Baseline Descriptive Analyses

Demographic characteristics, including age (years), sex, race, ethnicity, and other baseline characteristics, will be summarized descriptively by treatment group and overall. Medical history (coded using the Medical Dictionary for Regulatory Activities [MedDRA]) and prior and concomitant medications (coded using WHODrug) will be summarized by treatment and overall.

The numbers of subjects who were enrolled and completed each visit of the study will be provided, as well as the reasons for all enrollment discontinuations, grouped by major reasons (e.g., lost to follow-up). A list of discontinued subjects, protocol deviations, and subjects excluded from the analysis sets will be provided as well.

Exposure to IP and adherence to the dosing schedule will be summarized by treatment and overall.

CONFIDENTIAL

9.4.2 Efficacy Analyses

Summary descriptive statistics will be presented for all study visits at which efficacy data are collected. Efficacy analyses will be presented for the study eye and will only include data from before the earliest observed instance of rescue therapy. In other words, data that occurs after the earliest observed rescue therapy will be set to missing.

Efficacy analyses will be conducted using the FAS, in general, and sensitivity analyses for primary and secondary endpoints will be conducted using the PP Analysis Set.

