9.8 Missing, Unused, or Spurious Data

Missing data for continuous endpoints will be considered missing at random with the analysis using mixed model repeated measures. Otherwise, observed data will be analyzed at each visit.

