#### **9.7.1.5. Analysis of Efficacy**

Summary descriptive statistics will be presented for all study visits at which efficacy data are collected. Efficacy analyses will be presented by the study eye.

For subjects who discontinue treatment prior to the Visit 7, the data collected on the Early Termination eCRFs will not be summarized unless the termination within the visit windows of a particular visit.

All longitudinal models will be fit using the MIXED procedure in SAS. Categorical analyses will be conducted using the FREQ procedure.

Secondary and exploratory endpoints will be analyzed in a similar manner to the primary endpoint regardless of the significance of the primary endpoint analysis. All efficacy analyses will be conducted using the FAS and PP Analysis Sets.

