#### Intercurrent Events and Strategies to Address Intercurrent Events

- Discontinuation of study therapy with continued participation in the study without receipt of rescue therapy
  - Treatment Policy Approach – no imputation; use observed data
- Receipt of rescue therapy (topical corticosteroid) in the study eye
  - Composite Approach – subjects who receive rescue therapy ~~at or~~ before the assessment visit will be assumed to have failed the primary endpoint
- Missing data due to discontinuation due to Lack of Efficacy or Adverse Event
  - Composite Approach – subjects who discontinue due to Lack of Efficacy or Adverse Event before the assessment visit will be assumed to have failed the primary endpoint
- Missing data with or without withdrawal, regardless of reason
  - Hypothetical Approach – no imputation; analysis will be based on subjects who have an evaluable anterior chamber in the study eye at Visit 6 (Day 14)

Pearson's chi-square will be used to test the primary endpoint between the 2 different doses of VVN461 vs the Vehicle. Analyses will be also performed on observed data without failure criteria for rescue. These analyses will also be performed on the PP Analysis Set.

A sensitivity analysis with control-based multiple imputation method will be carried out in the following three steps:

- 1) Imputation: Missing binary data will be filled in 25 different times to generate 25 imputed datasets. The following code will be used to impute the 25 datasets with data of subjects prior to rescue medications.

[figure not shown]
The control is where treatment = 3. This imputes data for all arms according to the control treatment.

- 2) Analysis: Each of the 25 imputed datasets will be analyzed at Visit 6 using PROC FREQ where the proportions of responders in each treatment arm will be calculated:

[figure not shown]

- 3) Pooling: The results from the 25 imputed datasets will be combined for estimation using PROC MIANALYZE.

Results will include treatment arm proportions:

As well the difference between proportions:

The sensitivity analyses will only be performed on the primary endpoint at Visit 6. All analyses will each be performed with the FAS and Per Protocol Analysis Sets.

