### **9.8.2. Changes from Protocol-Specified Analyses**

Exploratory Efficacy Analysis:

- 1) Observed analysis of NPRS
- 2) Mean NPRS analysis using mixed model repeated measures

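### The documents do not give one rule for rescued subjects in the ACC, ACF and pain responder endpoints other than the primary: read literally the protocol drops them, while other text counts them as failures

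*Protocol*

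**What the plan says.** **Text that removes rescued subjects.** Protocol 9.4.2, which heads all the efficacy analyses, keeps only data from before the first rescue and adds: "In other words, data that occurs after the earliest observed rescue therapy will be set to missing". For endpoints outside the repeated-measures models, Protocol 9.8 says: "Otherwise, observed data will be analyzed at each visit". The SAP's missing-data paragraph repeats this, and its general conventions base percentages on subjects with available data unless otherwise noted.

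**Text that counts them as failures.** The estimand in Protocol 9.4.2.1 treats a rescued subject as having failed, but names only the primary endpoint. Protocol 5.5.2, repeated in SAP 9.5.1.2.3, counts subjects who need rescue as treatment failures and does not limit this to one endpoint. SAP 9.7.1.5 omits the general set-to-missing sentence and says: "Secondary and exploratory endpoints will be analyzed in a similar manner to the primary endpoint".

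**No rule stated.** Protocol 9.4.2.2 and SAP 9.7.1.5.2 (secondary endpoints) give no rescue rule. Nor do Protocol 9.7 and SAP 9.7.1.5.3 for the pain-free proportions.

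**The additional analysis.** SAP 9.7.1.5.1 adds: "Analyses will be also performed on observed data without failure criteria for rescue". It does not say whether grades recorded after rescue are included.

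**Declared changes.** SAP 9.8.2 lists an observed NPRS analysis and "Mean NPRS analysis using mixed model repeated measures". It lists nothing on rescue.

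**The concern.** Rescue happens after randomization and reflects poorly controlled inflammation. Leaving rescued subjects out of a responder proportion conditions on an outcome of treatment, so the comparison is no longer between randomized groups. Counting them as failures keeps every observed subject in the comparison. The two rules target different quantities and agree only when nobody is rescued before the assessment.

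Five endpoints are exposed: ACC Grade 0 at Day 7, ACF Grade 0 at Days 7 and 14, and pain-free at Days 7 and 14. The Day 7 endpoints are exposed only to rescue by then. The fourth secondary endpoint, the proportion needing rescue, does not use post-rescue assessments. The additional primary-endpoint analysis is also unclear. If the protocol's rule applies, it covers only subjects not rescued by Visit 6; if not, it covers every subject with a recorded grade.

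**Working it through.** **Inputs.** Protocol 9.2 gives 30 per group, "assuming a response rate of 30% in the Vehicle group", "the study will have 80% power to detect a difference of 35" points and "a two-sided 0.05 significance level for a Pearson chi-square test". The implied active rate is 30% + 35 points = 65%.

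**The plan's own figure.** The normal approximation gives power of 79.0%; the exact binomial power of the uncorrected Pearson chi-square is 79.8%. Both agree with the stated 80%. For dropout, 30/0.90 = 33.3, rounded up to 34 per arm, or 102 in total, as stated. The sample size is not in question.

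**Assumptions for the illustration.** The documents give no rescue rate, and no planning rates for the five endpoints. I borrow 30% v 65% as the rates when rescue counts as failure, take 30 per arm, and assume every rescued subject is a non-responder. Expected responders are 30 × 0.30 = 9 on Vehicle and 30 × 0.65 = 19.5 on active.

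**Formula.** If *v* Vehicle and *a* active subjects are rescued and dropped, the observed rates become 9/(30 − *v*) and 19.5/(30 − *a*).

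| Rescued, Vehicle/active | Vehicle rate | Active rate | Difference (points) | Exact power |
|---|---|---|---|---|
| 0/0 | 9/30 = 30.0% | 19.5/30 = 65.0% | 35.0 | 79.8% |
| 3/1 | 9/27 = 33.3% | 19.5/29 = 67.2% | 33.9 | 72.4% |
| 6/2 | 9/24 = 37.5% | 19.5/28 = 69.6% | 32.1 | 64.6% |
| 9/2 | 9/21 = 42.9% | 19.5/28 = 69.6% | 26.8 | 49.4% |
| 12/3 | 9/18 = 50.0% | 19.5/27 = 72.2% | 22.2 | 32.9% |
| 3/2 | 9/27 = 33.3% | 19.5/28 = 69.6% | 36.3 | 80.9% |
| 6/4 | 9/24 = 37.5% | 19.5/26 = 75.0% | 37.5 | 82.4% |
| 9/6 | 9/21 = 42.9% | 19.5/24 = 81.3% | 38.4 | 76.2% |
| 6/6 | 9/24 = 37.5% | 19.5/24 = 81.3% | 43.8 | 90.5% |

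**Direction.** Dropping rescued subjects raises the Vehicle rate by 0.30 × *v*/(30 − *v*) and the active rate by 0.65 × *a*/(30 − *a*). The difference shrinks only if the first exceeds the second, that is, if the odds of rescue on Vehicle exceed 0.65/0.30 = 2.17 times those on active. At 3/1 the odds ratio is (3/27)/(1/29) = 3.22 and the difference shrinks. At 9/6 it is (9/21)/(6/24) = 1.71 and the difference grows, although Vehicle has more rescue.

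**The case against.** The strongest reply is that the documents already answer the question. Protocol 5.5.2 makes rescued subjects treatment failures without restriction. Protocol section 9 leaves the technical detail to the SAP, and the SAP drops the general set-to-missing sentence and handles the other endpoints like the primary. Where the SAP wants pre-rescue data only, it says so: in the multiple imputation, the mean NPRS summary and the repeated-measures models.

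Much of this stands. A reader might infer that the protocol plainly excludes rescued subjects; it does not, because 5.5.2 says otherwise. The protocol contradicts itself. But 5.5.2 is the rescue-medication section, whereas 9.4.2 is the explicit analysis rule. The SAP's similar-manner sentence is general, and its available-data denominator and observed-data sentence pull the other way. Two careful programmers could still produce different tables.

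A reader might also infer that dropping rescued subjects always favours the arm with more rescue. The rows 3/2, 6/4 and 9/6 show otherwise.

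The power figures are borrowed from Day 14 ACC Grade 0. The five endpoints have no stated power and the SAP calls their p-values nominal, so the power column shows sensitivity to the rule, not a loss of planned power.

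Finally, the additional analysis may be read as certainly using post-rescue grades, or as certainly confined to never-rescued subjects. The first is the more natural reading, but the SAP's words establish neither.

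**Conclusion.** The point holds as an unresolved contradiction about five responder endpoints and an unclear additional analysis, with no declared change in SAP 9.8.2. Under the stated assumptions, the choice between dropping rescued subjects and counting them as failures moves a 35-point difference to anywhere between 22.2 points (12/3 rescued) and 43.8 points (6/6) in the scenarios shown. The true size depends on rescue rates that the documents do not give, and is smaller at Day 7 if most rescue comes later.

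It would be wrong to conclude that the main result is at risk. Both documents apply the failure rule to the primary endpoint, so its main analysis and Type I error control are untouched by this point. The change should be made before unmasking, because the bias can go in either direction.

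**What to change.** 1. In Protocol 9.4.2 and SAP 9.7.1.5 and 9.7.1.5.2, state that for every ACC, ACF and pain responder endpoint a subject rescued by the assessment, under the common definition in item 4, is a non-responder and stays in the denominator.
2. Limit set-to-missing after rescue to the mean-change and mean-NPRS analyses and to the pre-rescue input of the multiple imputation in SAP 9.7.1.5.1.
3. State that the additional analysis without the rescue failure rule uses every Visit 6 grade recorded, including after rescue.
4. Reconcile the analysis definition of rescue and apply one definition throughout. On timing, Protocol 9.4.2.1 includes rescue at the assessment visit, while SAP 9.7.1.5.1 shows those words struck out and leaves only rescue before it. On type, the estimand names topical corticosteroid in the study eye, while Protocol 5.5.2 covers any treatment the investigator finds appropriate.
5. List these points in SAP 9.8.2.

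The cost is wording and minor programming. No new data are needed: slit lamp examination is scheduled at every visit from Day 1, Protocol 5.5.2 asks that rescued subjects stay for safety evaluation, and SAP 9.7.1.6 already summarizes safety data after rescue. The downside is slightly lower reported response rates in every arm with rescue.
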